4.9.3 Multiple Values

For summaries displayed by visit, multiple values for a given assessment within a time window will be handled as follows:

Efficacy

The nearest non-missing assessment to the nominal timepoint will be assigned to the visit. If two or more values are equidistant from the nominal timepoint, then the latest assessment will be selected.

Safety

The assessment with the worst result will be assigned to the visit.

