4.8.4 Laboratory Data

4.8.4.1 Safety Laboratory Parameters

All laboratory data will be converted to SI units. The International Standard for the Handling and Reporting of Laboratory Data COG 3007 will be used to implement reference ranges and marked abnormalities for laboratory data where possible. Additionally, serum creatinine, hemoglobin, albumin and hematocrit will be presented in conventional units.

Summary statistics for the absolute and change from baseline values will be produced by visit for laboratory parameters.

Marked abnormalities will be summarized for laboratory parameters. Summaries by National Cancer Institute Common Terminology Criteria for Adverse Events (NCI CTCAE) grade will also be produced for certain lab assessments, including shift tables from baseline to highest grade post-baseline.

Shift tables from baseline to highest NCI CTCAE grade post-baseline will be produced for liver function laboratory tests.

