4.8.5 Vital Signs

Vital signs are measured at each scheduled visit in accordance with the schedule of assessments (see protocol). At infusion visits, vital signs should be taken pre-infusion, then every 15 minutes for 1 hour, then every 30 minutes until the end of the infusion, and within 30 minutes post-infusion. Additional readings may be obtained at the discretion of the investigator in the event of an infusion-related reaction.

Summary tables for the absolute value and change from baseline in vital sign assessments will be presented by visit. Vital sign assessments include respiratory rate, pulse rate, temperature, systolic and diastolic blood pressure. Body mass index will be calculated for these time points that body weight is measured.

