4.9 DATA HANDLING METHODS

4.9.1 Presentation of Data

Data displays include listings, tables, and plots. All data displays will be presented by treatment group.

Data presented in summary tables will be displayed using summary statistics. Continuous data will include number of patients, mean, standard deviation, median, minimum, and maximum. Categorical data will include the number and percentage of patients.

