4.9.2 Definitions

Baseline

Baseline is defined as the last non-missing value prior to receipt of study treatment. Typically, baseline will be the pre-dose Day 1 assessment, but may include screening results if the pre-dose Day 1 result is not available or missing. If the Day 1 or screening result is missing, then no imputation will be made and the baseline result will be set to missing.

Study Day

For each patient, the first day of study treatment will be designated study Day 1. Each subsequent assessment will be assigned a study day calculated as:

$$\text{date of assessment} - \text{date of first dose} + 1$$

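### By-visit safety means set the worst value in a window against a single unselected baseline, so within-arm mean change shifts towards worse wherever a window holds more than one value

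*SAP*

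**What the plan says.** SAP 4.9.3 opens with its scope: "For summaries displayed by visit, multiple values for a given assessment within a time window will be handled as follows". For efficacy the choice ignores the result: "The nearest non-missing assessment to the nominal timepoint will be assigned to the visit", with ties going to the latest assessment. For safety the choice depends on the result: "The assessment with the worst result will be assigned to the visit".

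Baseline is not selected in this way. SAP 4.9.2: "Baseline is defined as the last non-missing value prior to receipt of study treatment".

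The outputs that use these visit values are:
- SAP 4.8.4.1: "Summary statistics for the absolute and change from baseline values will be produced by visit for laboratory parameters".
- SAP 4.8.4.2: immunoglobulin values and changes from baseline by visit, plots of the mean over time, and the proportion below the lower limit of normal per visit.
- SAP 4.8.5: "Summary tables for the absolute value and change from baseline in vital sign assessments will be presented by visit".
- SAP 4.9.1, for all of these: "Continuous data will include number of patients, mean, standard deviation, median, minimum, and maximum".

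How many values a window can hold is clearest for dosing days, where SAP 4.8.5 sets this schedule: "vital signs should be taken pre-infusion, then every 15 minutes for 1 hour, then every 30 minutes until the end of the infusion". One more reading follows within 30 minutes after the infusion, and extra readings are possible if a reaction occurs. SAP 4.5 uses continuous windows running from midpoint to midpoint between visits, into which unscheduled and withdrawal visits may be mapped.

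**The concern.** A mean change from baseline is read as a typical patient's movement. That reading needs the two values being subtracted to be chosen in the same way. Here the post-baseline value is the extreme of everything in the window, while baseline is simply the last value before dosing. The difference has a non-zero expectation even if nothing has changed.

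The size of the artefact depends on how often a patient was measured. Vital-sign means would jump at infusion visits and fall back at visits with one reading, and that pattern could be taken for an infusion effect. In laboratory and immunoglobulin tables, patients sampled more often contribute more extreme values.

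SAP 4.9.3 also does not say which direction is worst for measures where both high and low are abnormal, such as blood pressure, temperature or potassium.

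**Working it through.** The plan states no figure on this point, so there is none to reproduce.

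**Step 1. Does any text limit the rule?** SAP 4.9.3 applies it to by-visit safety summaries in general. Nothing in SAP 4.8.4.1, 4.8.4.2, 4.8.5 or 4.9.1 restricts it to categorical tables, names the pre-infusion reading as the visit value, or applies the same selection to baseline.

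**Step 2. Readings per infusion visit.** Protocol Appendix 7, Table 2 gives 195 minutes for the second and later infusions. Under the SAP 4.8.5 schedule:
- pre-infusion: 1
- 15, 30, 45 and 60 minutes: 4
- 90, 120, 150 and 180 minutes: 4
- post-infusion: 1

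The total is 10. The 255-minute schedule (Appendix 7, Table 1) gives about 12, but that is the first infusion, on Day 1, which is the baseline visit. At later visits the slower schedule applies only after a previous reaction.

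**Step 3. Expected shift with no drug effect.** Write each reading as patient mean + day effect + residual. Let σ be the within-patient SD, ρ the correlation between same-day readings within a patient, and E[max of k] the expected largest of k independent standard normal values. One unselected baseline has expected deviation 0, so

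shift = E[max of k] × σ × √(1 − ρ).

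The documents give neither σ nor ρ. Results are therefore in units of σ, over an assumed range of ρ, with normal readings.

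| k | E[max of k] | ρ = 0 | ρ = 0.5 | ρ = 0.7 |
|---|---|---|---|---|
| 1 | 0 | 0 | 0 | 0 |
| 10 | 1.539 | 1.54 | 1.539 × 0.707 = 1.09 | 1.539 × 0.548 = 0.84 |

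A simulation with no drug effect (60 patients in an arm, 4,000 runs) gave 1.54 at ρ = 0 and 1.09 at ρ = 0.5 for k = 10. With one unselected value it gave −0.002.

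**Step 4. Laboratory data and immunoglobulins.** One sample is scheduled per visit, so a second value comes from an unscheduled or withdrawal sample. The documents do not say how often this happens. If a share f of patients has two independent values, shift = f × E[max of 2] = f × 0.564:
- f = 10%: 0.06 SD
- f = 30%: 0.17 SD

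**Step 5. Between arms.** With equal counts the shifts cancel and the difference is 0. With an assumed 14 versus 10 independent readings it is 1.703 − 1.539 = 0.16 SD. With an assumed 20% versus 10% of patients having a second laboratory value it is 0.10 × 0.564 = 0.06 SD.

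**The case against.** The strongest reply is that taking the worst safety value is deliberately conservative, that placebo is shown alongside under the same rule, and that no hypothesis test is planned on these tables. This stands in part. Conservatism is right for tables of abnormalities, and with equal measurement the arm contrast is clean. It does not rescue the within-arm mean change, which is what the tables display.

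Several stronger readings are tempting but are not supported:

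- *The arms will differ because reactions prompt extra readings on obinutuzumab.* This is possible, but the documents do not show it. Protocol 5.1.1 reports, from the haematological studies, that reactions occurred mainly with the first 1000 mg and that most patients had none later. Extra readings should then be least common at the post-baseline infusions.
- *Laboratory means are generally distorted.* They are distorted only to the extent that patients have repeat samples, and that frequency is not given.
- *Vital-sign trends cannot be recovered at all.* Protocol 6.5.4 already plans change from the reading just before each infusion. That does not alter the SAP's by-visit rule, but it supplies an unselected comparator.
- *All readings on an infusion day must be pooled.* This follows from the rule as written. SAP 4.9.3 does not mention infusion readings, so the authors may have intended otherwise.

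The direction of worst for laboratory tests may be settled in the laboratory-data standard that SAP 4.8.4.1 cites, which is not available here. That reference does not cover vital signs.

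**Conclusion.** The point holds as a within-arm bias. As SAP 4.9.3 is written, mean change from baseline moves towards worse with no drug effect wherever a window holds more than one value.

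For vital signs at Days 15, 168 and 182 the shift is about 0.8 to 1.5 within-patient SD. This rests on about 10 pooled readings and assumed correlations of 0.7 to 0; higher correlation would make it smaller. For laboratory data and immunoglobulins it is about 0.06 to 0.17 SD if an assumed 10% to 30% of patients have a second, independent value, and zero for patients without one.

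A reader might go further and infer a biased treatment comparison. That would require reading counts to differ by arm, which the documents do not establish. Efficacy is unaffected, because it uses the nearest value. Laboratory shift tables to the highest post-baseline grade are meant to show extremes and are not at fault.

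**What to change.** 1. **SAP 4.9.3.** For by-visit means, mean plots and changes from baseline, use the scheduled value nearest the nominal day, and the pre-infusion reading on dosing days. State the second part explicitly. Readings on one infusion day are equally distant from the nominal day, and the efficacy tie rule would take the latest, not the pre-infusion one.
2. **Worst values.** Keep them for the laboratory marked-abnormality, CTCAE and shift tables. State the direction, with high and low shown separately for two-sided measures.
3. **SAP 4.8.5.** Add the proportion of patients with abnormal vital signs, which SAP 2.2.4 lists as an outcome, and the change from the pre-infusion reading during and after infusion, which Protocol 6.5.4 plans. This step is needed because SAP 4.8.4.1 plans abnormality and shift tables for laboratory data only. Without it, step 1 would drop in-infusion extremes from the SAP's vital-sign summaries.

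The cost is SAP wording and a little extra programming. By-visit means will look less extreme. No new data are needed.

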4.10 MISSING DATA

Methods for handling missing data for efficacy analyses are described in detail throughout Section 4.6.1. Missing or partial dates for AEs, concomitant medications (except oral corticosteroids), laboratory assessments, and medical history will be imputed as detailed in [Appendix 3](#).

4.11 INTERIM ANALYSES

4.11.1 Pharmacodynamic Futility Interim Analysis

An interim analysis for futility is planned on the basis of CD19 B-cell counts after 30 patients have been assigned to the obinutuzumab arm and have had their Day 28 blood CD19⁺ B-cell counts assessed by high-sensitivity flow cytometry (HSFC). The effect of rituximab on CD19⁺ B-cell counts has been measured by HSFC in an investigator sponsored study in which peripheral B-cell depletion below the lower limit of quantification (LLOQ) of the assay occurred in 46% of patients. Slightly less than half of these rituximab treated patients with full peripheral B-cell depletion achieved a major clinical response, with the remainder of the patients having partial clinical responses. Therefore, it is hypothesized that an improved outcome over rituximab is achievable for a LN patient population with full peripheral B-cell depletion, with the assumption that improved tissue depletion with treatment will parallel the peripheral depletion. To test the hypothesis in this study, we will require at least 50% of the obinutuzumab-treated patients to have peripheral B-cell depletion below the LLOQ of the HSFC assay in order to have a realistic chance of a positive primary endpoint analysis for the treatment arm. Quantification of the link between this biomarker and the study's primary analysis has not been established; therefore, predictive probabilities for study statistical significance cannot be provided. Consequently, the study will be terminated if the 5% one-sided Clopper-Pearson upper confidence limit for the proportion of patients who achieve B-cell depletion is not greater than 0.5. Assuming that there are 30 patients at the time of the interim analysis, this will effectively require that ≥ 11 obinutuzumab patients have complete B-cell depletion below the LLOQ of the HSFC assay at the time of the interim analysis.

The interim analysis will be performed by the iDMC, which may recommend that the study be stopped for futility if the futility criterion is satisfied. Additional criteria for recommending that the study be stopped for futility may be added to the iDMC Charter. As this interim analysis will only result in termination of the study due to futility and not for efficacy, an adjustment to the α -level is not required. Although the outcome of the interim analysis may reduce the power of this study to below the estimated 83%, a sample size adjustment has not been made.

4.11.2 Renal Response Interim Analysis

The iDMC will also conduct an interim efficacy analysis to evaluate renal response when the last patient has achieved the 6-month visit. The interim analysis will be performed by the iDCC and interpreted by members of the iDMC. The iDMC may recommend to the Sponsor to consider the planning of Phase III if the treatment difference (obinutuzumab minus placebo) in complete renal response at Week 24 is $\geq 10\%$. In addition, the iDMC will inform the Sponsor if the treatment difference (obinutuzumab minus placebo) in complete renal response at Week 24 is $\geq 20\%$.

Appendix 1 Protocol Synopsis

TITLE: A RANDOMIZED, DOUBLE-BLIND, PLACEBO-CONTROLLED, MULTI-CENTER STUDY TO EVALUATE THE SAFETY AND EFFICACY OF OBINUTUZUMAB IN PATIENTS WITH ISN/RPS 2003 CLASS III OR IV LUPUS NEPHRITIS

PROTOCOL NUMBER: WA29748

VERSION NUMBER: 4

EUDRACT NUMBER: 2015-002022-39

IND NUMBER: 125,054

NCT NUMBER: NCT02550652

TEST PRODUCT: Obinutuzumab (GA101; RO5072759)

PHASE: II

INDICATION: ISN/RPS Class III or IV Lupus Nephritis

SPONSOR: F. Hoffmann-La Roche Ltd

OBJECTIVES

EFFICACY OBJECTIVES

The primary efficacy objective for this study is as follows:

- To evaluate the efficacy of obinutuzumab compared with placebo in patients with International Society of Nephrology (ISN)/Renal Pathology Society (RPS) Class III or IV lupus nephritis (LN) as measured by complete renal response (CRR) at 52 weeks

The secondary efficacy objectives for this study are as follows:

- To assess overall renal response (defined as CRR plus partial renal response [PRR])
- To evaluate the ability of obinutuzumab to improve time-to-response (CRR plus PRR) over the course of 52 weeks

SAFETY OBJECTIVES

The safety objectives for this study are as follows:

- To evaluate the safety of obinutuzumab compared with placebo in patients with Class III or IV LN, focusing on the nature, frequency, and severity of serious and non-serious adverse events, as well as effects on laboratory values, vital signs, or other safety biomarkers
- To characterize the immunogenic potential of obinutuzumab by measuring human anti-drug antibodies and assessing their relationship with other outcome measures
- To fully characterize adverse events of special interest, including infusion reactions, infections, thrombocytopenia, and neutropenia

PHARMACODYNAMIC OBJECTIVE

The pharmacodynamic (PD) objective for this study is as follows:

Obinutuzumab—F. Hoffmann-La Roche Ltd

Statistical Analysis Plan

WA29748

- To compare changes in CD19+ B cells in the peripheral blood following treatment with obinutuzumab versus placebo

PHARMACOKINETIC OBJECTIVES

The pharmacokinetic (PK) objectives for this study are as follows:

- To characterize the pharmacokinetics of obinutuzumab in the LN population
- To assess potential PK interactions between obinutuzumab and concomitant medications, including mycophenolate mofetil (MMF)

PATIENT-REPORTED OUTCOME OBJECTIVES

The patient-reported outcome (PRO) objective for this study is as follows:

- To assess the change from baseline of the patient's general health over the course of the study by use of the Subject's Global Assessment

EXPLORATORY OBJECTIVES

The exploratory objectives for this study are as follows:

- To evaluate pre-dose levels of exploratory biomarkers (which may include but are not limited to B-cell subsets and levels of protein and mRNA in serum, plasma, blood, and urine) and potential associations with outcome
- To evaluate changes in exploratory biomarkers (which may include but are not limited to B-cell subsets and levels of protein and mRNA in serum, plasma, blood, and urine) over time in patients dosed with obinutuzumab versus patients dosed with placebo
- To evaluate the occurrence of extrarenal flares
- To evaluate the impact of therapy on patient and physician-reported outcomes
- To assess damage through the Glucocorticoid Toxicity Change Index (GTCI)
- To assess renal biopsy histopathology (for the presence and depletion of B cells at the screening biopsy and from subsequent biopsies)

Additional exploratory objectives and outcome measures will be included in a final Statistical Analysis Plan (SAP).

STUDY DESIGN

DESCRIPTION OF STUDY

This Phase II study is a parallel-group, double-blind, randomized, placebo-controlled study comparing the efficacy and safety of obinutuzumab plus MMF with placebo plus MMF in Class III and IV patients with proliferative LN. The Sponsor intends to enroll approximately 120 patients diagnosed with ISN/RPS Class III or IV LN, with a diagnosis of systemic lupus erythematosus (SLE) based on current American College of Rheumatology (ACR) criteria (at least 4 criteria must be present, one of which must be a positive anti-nuclear antibody [ANA]), in centers throughout the world. In addition to study treatment, patients will receive standard-of-care therapy with angiotensin-converting enzyme (ACE) inhibitors/angiotensin-II-receptor blockers, MMF (dosed at 2.0–2.5 g/day) or mycophenolic acid (MPA) (dosed 1440–1800 mg/day), and a prednisone taper. Patients must be 18–75 years of age and have ISN/RPS 2003 Class III or IV proliferative LN as evidenced by renal biopsy performed within 6 months prior to or during screening and may have concomitant Class V disease (e.g., Class III/V or Class IV/V). Patients with Class III (C) or Class IV (C) disease will be excluded because of the lower likelihood of response within these categories. Patients must exhibit significant proteinuria (urine protein to creatinine ratio > 1.0 based on a 24-hour urine collection). Key exclusions will be evidence of severe renal impairment (estimated glomerular filtration rate [GFR] < 30 mL/minute per 1.73 m² of body surface area), end-stage renal disease requiring dialysis or transplantation, evidence of active infections, and other safety-related exclusions. Patients will receive an initial 1000 mg of methylprednisolone intravenous (IV) prior to or during screening, and may receive up to a total of 3000 mg

Obinutuzumab—F. Hoffmann-La Roche Ltd

Statistical Analysis Plan

WA29748

methylprednisolone IV prior to randomization for severe clinical activity according to guidelines of routine care for these patients. Patients will receive 80 mg methylprednisolone (or methylprednisolone placebo) on the day of the obinutuzumab/placebo infusion to reduce infusion-related reactions. Oral corticosteroids will be initiated at a dose of 0.5 mg/kg (maximum 60 mg/day) and will be reduced over 10 weeks. This modified taper, from the LUNAR study, will be initiated at a lower dose in recognition that prednisone doses above 10 mg/day are associated with significant adverse events, including increased risk of cardiovascular events. Prior experience with rituximab suggests that it can potentially enable complete and PRRs in the absence of oral prednisone or a prednisone taper, thus allowing the use of lower doses of corticosteroids as proposed in this Phase II protocol.

Patients will be followed until at least Week 104, with the primary endpoint evaluation at Week 52. An interim analysis at 6 months will be performed to evaluate early differences in CRR. All patients will have central reading of the renal biopsy histopathology and will also receive repeat renal biopsy as available on the basis of clinical status and local practice. All patients will be evaluated by high-sensitivity flow cytometry (HSFC) to evaluate the ability of obinutuzumab to deplete circulating peripheral B cells, and an interim PD analysis will be performed to assess whether patients do not fully deplete peripheral CD19 B cells as anticipated. These mechanistic studies and more intensive histopathologic reviews are intended to test the hypothesis that greater B-cell depletion in the target organ (kidney) and associated secondary lymphoid structures will translate into greater CRR rates.

NUMBER OF PATIENTS

The study will enroll approximately 120 patients with active ISN/RPS 2003 Class III or IV LN at approximately sixty centers in North America, South America, Europe, and selected other countries.

TARGET POPULATION

Inclusion Criteria

Patients must meet the following criteria for study entry:

- Signed Informed Consent Form
- Age 18–75 years
- Ability to comply with the study protocol, in the investigator's judgment
- Diagnosis of SLE, according to current ACR criteria (at least four criteria must be present, one of which must be a positive ANA)
- Diagnosis of ISN/RPS 2003 Class III or IV LN as evidenced by renal biopsy performed within 6 months prior to or during screening. Patients may co-exhibit Class V disease in addition to either Class III or Class IV disease.
- Proteinuria (urine protein to creatinine ratio) >1.0, based on a 24-hour urine collection
- For women who are not postmenopausal (\geq 12 months of non-therapy-induced amenorrhea) or surgically sterile (absence of ovaries and/or uterus): agreement to remain abstinent or use two adequate methods of contraception, including at least one method with a failure rate of < 1% per year, during the treatment period and for at least 18 months after the last dose of study drug

Abstinence is only acceptable if it is in line with the preferred and usual lifestyle of the patient. Periodic abstinence (e.g., calendar, ovulation, symptothermal, or postovulation methods) and withdrawal are not acceptable methods of contraception.

Barrier methods must always be supplemented with the use of a spermicide.

Examples of contraceptive methods with a failure rate of < 1% per year include tubal ligation, male sterilization, hormonal implants, established, proper use of combined oral or injected hormonal contraceptives, and certain intrauterine devices.

- For men: agreement to remain abstinent or use a condom plus an additional contraceptive method that together result in a failure rate of < 1% per year during the treatment period and for at least 12 months after the last dose of study drug and agreement to refrain from donating sperm during this same period

Obinutuzumab—F. Hoffmann-La Roche Ltd

Statistical Analysis Plan

WA29748

Men with a pregnant partner must agree to remain abstinent or use a condom for the duration of the pregnancy.

Abstinence is only acceptable if it is in line with the preferred and usual lifestyle of the patient. Periodic abstinence (e.g., calendar, ovulation, symptothermal, or postovulation methods) and withdrawal are not acceptable methods of contraception.

Patients must be willing to practice this method of contraception while taking MMF and for 90 days after stopping MMF.

Exclusion Criteria

Patients who meet any of the following criteria will be excluded from study entry:

- Retinitis, poorly controlled seizure disorder, acute confusional state, myelitis, stroke or stroke syndrome, cerebellar ataxia, or dementia that is currently active and resulting from SLE
- Presence of rapidly progressive glomerulonephritis defined by
 - The presence of crescent formation in $\geq 50\%$ of glomeruli assessed on renal biopsy or
 - Sustained doubling of serum creatinine within 12 weeks of screening or
 - The investigator's opinion that the patient has rapidly progressive glomerulonephritis.
- Severe renal impairment as defined by estimated GFR < 30 mL/min or the need for dialysis or renal transplant
- Greater than 50% of glomeruli with sclerosis on renal biopsy
- Treatment with cyclophosphamide or calcineurin inhibitors within the 3 months prior to randomization
- Unstable disease with thrombocytopenia or at high risk for developing clinically significant bleeding or organ dysfunction requiring therapies such as plasmapheresis or acute blood or platelet transfusions
- Lack of peripheral venous access
- Pregnancy or lactation
- History of severe allergic or anaphylactic reactions to monoclonal antibodies or known hypersensitivity to any component of the obinutuzumab infusion
- Significant or uncontrolled medical disease in any organ system not related to SLE or LN, which, in the investigator's opinion, would preclude patient participation
- Concomitant chronic conditions, excluding SLE, (e.g., asthma, Crohn's disease) that required oral or systemic steroid use in the 52 weeks prior to screening
- Known HIV infection
- Known active infection of any kind (excluding fungal infection of nail beds) or any major episode of infection requiring hospitalization or treatment with IV anti-infectives within 8 weeks of the screening visit or oral anti-infectives within 2 weeks prior to the screening visit
- History of serious recurrent or chronic infection
- History of cancer, including solid tumors, hematological malignancies, and carcinoma in situ (except basal cell carcinomas of the skin that have been treated or excised and have resolved)
- Currently active alcohol or drug abuse or history of alcohol or drug abuse within 52 weeks prior to screening
- Major surgery requiring hospitalization within 4 weeks of randomization (excluding diagnostic surgery)
- Previous treatment with an anti-CD20–targeted therapy within 12 months of randomization
- Previous treatment with a biologic B-cell–targeted therapy (other than anti-CD20) within 6 months of randomization

Obinutuzumab—F. Hoffmann-La Roche Ltd

Statistical Analysis Plan

WA29748

- Treatment with any investigational agent within 28 days of randomization or five half-lives of the investigational drug (whichever is longer)
- Receipt of a live vaccine within 28 days prior to screening
- Intolerance or contraindication to oral or IV corticosteroids
- Aspartate aminotransferase or alanine aminotransferase $> 2.5 \times$ upper limit of normal (ULN)
- Amylase or lipase $> 2 \times$ ULN
- Neutrophils $< 1.5 \times 10^3/\mu\text{L}$
- Positive hepatitis B surface antigen (HBsAg) or hepatitis C serology. Patients who are HBsAg negative and hepatitis B core antibody positive with no detectable DNA will be allowed into the study but will require regular monitoring of hepatitis B virus DNA.
- Hemoglobin $< 7 \text{ g/dL}$, unless caused by autoimmune hemolytic anemia resulting from SLE
- Platelet count $< 10,000/\mu\text{L}$
- Positive serum human chorionic gonadotropin measured prior to the first obinutuzumab infusion
- Known intolerance to MMF and MPA

LENGTH OF STUDY

The study will follow all patients for a minimum of 78 weeks after the last infusion of obinutuzumab at Day 182. In consideration of recruitment and follow-up (independent of B-Cell follow-up [BCFU]), the length of study is estimated to be greater than 36 months. Patients may enter BCFU and continue to be evaluated for safety on a limited basis.

END OF STUDY

The end of this study is defined as the last patient's last visit at Week 104. This has been selected to enable 78 weeks (~18 months) of safety follow-up after the last dose of study drug to assess the occurrence of adverse events and to enable an assessment of peripheral blood CD19+ B cell return.

Additional B-cell follow-up (BCFU) visits will occur until patients have achieved their baseline CD19+ count or achieved 25 cells/ μL CD19+ count (the lower limit of normal (LLN) of CD19+ B cells for this lupus population), whichever occurs first. B-cell follow-up (BCFU) visits for all patients will end when the last patient has completed ~18 months of safety follow-up from the last dose of blinded obinutuzumab infusion.

Patients who receive additional therapies that reduce peripheral B-cell counts will not be included in BCFU.

OUTCOME MEASURES

PRIMARY EFFICACY OUTCOME MEASURE

The primary efficacy outcome measure is the proportion of patients who achieve a CRR, evaluated at 52 weeks.

CRR is defined by attainment of all of the following:

- Normalization of serum creatinine as evidenced by the following:
 - Serum creatinine \leq the ULN range of central laboratory values if baseline (Day 1) serum creatinine is above the ULN
 - Serum creatinine $\leq 15\%$ above baseline and \leq the ULN range of central laboratory values if baseline (Day 1) serum creatinine is \leq the ULN range of central laboratory values
- Inactive urinary sediment (as evidenced by < 10 RBCs/high-power field (HPF) and the absence of red cell casts)
- Urinary protein to creatinine ratio < 0.5

SECONDARY EFFICACY OUTCOME MEASURES

The secondary efficacy outcome measures are the following:

- Proportional analysis of patients who achieve an overall response at Week 52 (CRR + PRR)
- Time to overall response (CRR + PRR) over the course of 52 weeks
- Percent reduction or increase from baseline and mean and median assessments of biomarkers of LN disease activity (e.g., reduction in anti-dsDNA antibody levels, increase C3 and C4 levels)
- Proportion of patients that achieve a PRR at Week 52 as defined by attainment of all of the following:
 - Serum creatinine \leq 15% above baseline value
 - No urinary red cell casts and either RBCs/HPF \leq 50% above baseline or < 10 RBCs/HPF
 - 50% improvement in the urine protein to creatinine ratio, with one of the following conditions met:
 - If the baseline urine protein to creatinine ratio is ≤ 3.0 , then a urine protein to creatinine ratio of < 1.0
 - If the baseline protein to creatinine ratio is > 3.0 , then a urine protein to creatinine ratio of < 3.0
- Proportion of patients who achieve a CRR at Week 24
- Time to CRR, over the course of 52 weeks.
- Proportion of patients that achieve a modified CRR (mCRR1) at Week 52 employing the primary-efficacy measure definition and removing the urinary sediment analysis criteria
 - mCRR1 is defined by attainment of normalization of serum creatinine as evidenced by the following:
 - Serum creatinine \leq the ULN range of central laboratory values if baseline (Day 1) serum creatinine is above the ULN
 - Serum creatinine $\leq 15\%$ above baseline and \leq the ULN range of central laboratory values if baseline (Day 1) serum creatinine \leq the ULN range of central laboratory values
 - Urinary protein to creatinine ratio < 0.5
- Proportion of patients that achieve a second modified CRR (mCRR2) at Week 52 as defined by attainment of the following:
 - Normalization of serum creatinine as evidenced by the following:
 - Serum creatinine $\leq 15\%$ above baseline if baseline (Day 1) serum creatinine is above the normal range of the central laboratory values or \leq the ULN range of central laboratory values if baseline (Day 1) serum creatinine is \leq the ULN range of central laboratory values
 - Inactive urinary sediment (as evidenced by < 10 RBCs/HPF and the absence of red cell casts)
 - Urinary protein to creatinine ratio < 0.5
- Proportion of patients that achieve a third modified CRR (mCRR3) at Week 52 as defined by attainment of the following:
 - Normalization of serum creatinine as evidenced by serum creatinine \leq the ULN range of central laboratory values
 - Urinary protein to creatinine ratio < 0.5

The hierarchical ordering of the secondary endpoints will be pre-specified in the SAP.

SAFETY OUTCOME MEASURES

The safety outcome measures for this study are as follows:

- Incidence, type, and severity of adverse events

Obinutuzumab—F. Hoffmann-La Roche Ltd

Statistical Analysis Plan

WA29748

- Abnormal vital signs
- Abnormal laboratory values

Safety will be monitored through regular physical examinations, vital signs, hematologic and chemistry laboratory tests, urinalyses, and incidence and severity of adverse events. In addition, the following will be examined:

- Circulating B cells, T cells, neutrophils and other cell populations
- Plasma immunoglobulins (total Ig, IgG, IgM, and IgA)
- Record of menses
- Pregnancy
- Antibody titers for mumps, rubella, *Varicella*, tetanus, influenza, and *Streptococcus pneumoniae*

PHARMACODYNAMIC OUTCOME MEASURE

The primary PD outcome measure for this study is as follows:

- Changes in levels of circulating CD19+ B-cells relative to baseline

PHARMACOKINETIC OUTCOME MEASURES

The obinutuzumab PK outcome measures for this study are as follows:

Non-linear mixed-effects modeling (with software NONMEM) will be used to analyze the dose-concentration-time data of obinutuzumab. The PK profile data will be used to further develop a PK model, including the effect of major covariates (e.g., sex, race/ethnicity, weight, biochemical and hematological parameters at baseline, degree of underlying disease), on the main parameters (e.g., clearance). The derivation of individual measures of exposure, such as area under the concentration-time curve and maximum concentration observed will depend on the final PK model used for this analysis. Results of this analysis may be reported separately. Serum obinutuzumab will be summarized (mean, minimum, maximum, SD, and geometric mean) and reported within this study.

Exploratory graphical analyses will be performed to assess whether the occurrences of serious adverse events and abnormalities in the safety laboratory parameters in patients treated with obinutuzumab can be attributed to obinutuzumab exposure. Also, exploratory graphical analyses will be performed to assess whether the variability in response can be attributed to the variability in obinutuzumab exposure. Relevant observed relationships between exposure and safety parameters may be further characterized using different approaches such as logistic regression analysis and indirect response modeling.

Additional PK and PD analyses may be conducted as appropriate.

PATIENT-REPORTED OUTCOME MEASURE

The PRO measure for this study is as follows:

- Subject's Global Assessment

This visual analog scale (VAS) will be captured in screening, at the baseline visit, and at several timepoints during study conduct.

EXPLORATORY OUTCOME MEASURES

The exploratory outcome measures for this study are as follows:

- Changes in levels of circulating B-cell subsets relative to baseline
- Changes in levels of exploratory biomarkers, which may include but are not limited to levels of protein and mRNA in serum, plasma, blood, and urine, relative to baseline
- Proportion of patients experiencing a Systemic Lupus Erythematosus Disease Activity Index-2K flare
- Proportion of patients experiencing a renal flare over 52 weeks and 104 weeks

Obinutuzumab—F. Hoffmann-La Roche Ltd

Statistical Analysis Plan

WA29748

- Proportion of patients achieving CRR, mCRR1, mCRR2, and mCRR3 at additional timepoints, including Week 12 and Week 36
- Physician's Global Assessment

This VAS will be captured in screening, at the baseline visit, and at several timepoints during study conduct.
- GTCI
- Renal biopsy evaluations

INVESTIGATIONAL MEDICINAL PRODUCTS

TEST PRODUCT (INVESTIGATIONAL DRUG)

The test product for this study is obinutuzumab and will be administered by IV infusion at a dose of 1000 mg on Days 1, 15, 168, and 182. The study drug will be administered in a hospital or clinic environment where full resuscitation facilities are immediately available and under close supervision of the investigator or designee. After the end of the first infusion, the IV line will remain in place for at least 2 hours to enable administration of IV drugs if necessary. If no adverse events occur during this period of time, the IV line may be removed. For subsequent infusions, access through an IV line should remain in place for at least 30 minutes from the end of the infusion, and if no adverse events occur after 30 minutes, the IV access may be removed.

COMPARATOR (PLACEBO)

The obinutuzumab placebo (corresponding to the obinutuzumab 1000-mg dose) will be administered by IV infusion on Days 1, 15, 168, and 182. The placebo will be administered in a hospital or clinic environment where full resuscitation facilities are immediately available and under close supervision of the investigator or designee. After the end of the first infusion, the IV line will remain in place for at least 2 hours to enable administration of IV drugs if necessary. If no adverse events occur during this period of time, the IV line may be removed. For subsequent infusions, access through an IV line should remain in place for at least 30 minutes from the end of the infusion, and if no adverse events occur after 30 minutes, the IV access may be removed.

NON-INVESTIGATIONAL MEDICINAL PRODUCTS

